4.10.5 Electrocardiograms

On Days 1 and 14, resting 12-lead ECG data will be collected at the following timepoints: predose and at 0.5, 1.0, 1.5, 2.0, 2.5, 3.0, 4.0, 8.0, 12.0 and 24.0 hours (all +/- 15 mins).

The same assessment schedule is also required on Day -1, starting at a time similar to that planned for Days 1 and 14. The Day -1 and Day 1, 24 hour ECGs must be performed prior to the dose of study medication the following morning (on Days 1 and 2, respectively).

Once-daily ECG recordings will be just prior to dosing (approx. 30 mins) on all other days during the inpatient stay (Days 3 to 8).

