8.10.1 Twice Daily Hot Flash Paper Diaries

8.10.1.1 Frequency of Hot Flashes

Frequency by day

Daily (24-hour) frequency of hot flashes for Day Y will be equal to the number of hot flashes recorded on Day Y (day time hot flushes recorded in the evening + night time hot flushes recorded the following morning).

The daily frequency of mild, moderate, severe, moderate/severe, and total hot flashes will be summarized for each day. The mean (\pm SE) frequency of mild, moderate, severe, moderate/severe (moderate and severe combined), and total hot flashes will be displayed graphically by day (Day -8 onwards).

Average daily frequency by week

The average daily frequency of hot flashes for each of Week -1, Week 1, and Week 2 will be equal to the average of the daily frequency of hot flashes from Day -8 to Day -2 inclusive, from Day 1 to Day 7 inclusive, and from Day 8 to Day 14 inclusive, respectively.

The average daily frequency by week and the change from Week -1 (for Week 1 and Week 2) of mild, moderate, severe, moderate/severe, and total hot flashes will be summarized descriptively by treatment.

Statistical analysis

The analysis will test the treatment difference of change in the average daily frequency of moderate/severe hot flashes from Week -1 to each of Week 1 and Week 2.

The analysis will be based on a linear mixed-effects model with the change from Week -1 as a dependent variable, treatment, week, treatment-by-week interaction as fixed effects, subject as a random effect, and baseline (frequency of moderate/severe hot flashes at Week -1) and baseline-by-week interaction as covariates. Subjects dosed with placebo will be analyzed as a pooled group. An unstructured covariance matrix will be specified for the repeated measures at postdose timepoints for each subject. From this analysis, the least-squares (LS) mean and 2-sided 90% CIs will be calculated for the contrast “NT-814 versus placebo” for each treatment and each postdose week, separately.

Following is the SAS code for reference:

```
proc mixed data=dataset ;  
class TRT <50 mg NT-814, 100 mg NT-814, 150 mg NT-814, etc... , placebo> WEEK <1,2> USUBJID;  
model CHG = TRT WEEK TRT*WEEK BSL BSL*WEEK / s ddfm=kr;  
random USUBJID;  
repeated WEEK / type=un subject=USUBJID;  
lsmeans TRT*WEEK / cl diff alpha=0.1;  
run;
```

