The analysis for QTcF will be based on a linear mixed-effects model with change-from-baseline QTcF (Δ QTcF) as the dependent variable, time (categorical), treatment (each NT-814 dose group and all placebo group), and time-by-treatment interaction as fixed effects, and baseline QTcF as a covariate. Baseline will be the derived QTc intervals from the ECG timepoint recorded predose on Day 1. Subjects dosed with placebo will be analyzed as a pooled group. An unstructured covariance matrix will be specified for the repeated measures at postdose timepoints for each subject. If the model with unstructured covariance matrix fails to converge, other covariance matrix such as autoregressive and compound symmetry will be considered. From this analysis, the LS mean and 2-sided 90 % CIs will be calculated for the contrast “NT-814 versus placebo” at each treatment and each postdose timepoint, separately. These analyses will be performed using the QT/QTc population.

For HR, PR, QTcB, QT, RR, and QRS intervals, the analysis will be based on the change-from-baseline post-dosing (Δ HR, Δ PR, Δ QTcB, Δ QT, Δ RR, and Δ QRS). The same model will be used as described for QTcF. The LS mean, SE and 2-sided 90% CI from the statistical modeling for both change-from-baseline and placebo-corrected change-from-baseline values will be listed in the tables and graphically displayed.

Categorical Analyses

The analyses results for categorical outliers, T-wave morphology and U-wave presence will be summarized in frequency tables with counts percentages for both number of subjects and number of timepoints. For categorical outliers, the number (percentage) of subjects as well as timepoints who had increases in absolute QTc (QTcF and QTcB) values >450, 480, and 500 msec, and changes from predose baseline of >30 or >60 msec; increase in PR from predose baseline >25% to a PR >200 msec; increase in QRS from predose baseline >25% to a QRS >120 msec; decrease in HR from predose baseline >25% to a HR <50 bpm; and increase in HR from predose baseline >25% to a HR >100 bpm will be determined. For T-wave morphology and U-wave presence, the analyses will be focused on change from baseline (i.e., treatment-emergent changes). These analyses will be performed using the QT/QTc population.

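### The by-timepoint ECG models adjust only for the Day 1 predose timepoint and leave out about 10 pre-randomisation ECG timepoints per woman from Day -1, which costs some precision but causes no bias

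*SAP*

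**What the plan says.** The By-Timepoint Analysis in SAP section 8.11.7 models change from baseline QTcF with time, treatment, "time-by-treatment interaction as fixed effects, and baseline QTcF as a covariate". Baseline is defined there as follows: "Baseline will be the derived QTc intervals from the ECG timepoint recorded predose on Day 1". Only post-dose readings are modelled as outcomes: "An unstructured covariance matrix will be specified for the repeated measures at postdose timepoints for each subject". For HR, PR, QTcB, QT, RR and QRS, "The same model will be used as described for QTcF". Placebo women are pooled across cohorts, and each dose is compared with placebo by a two-sided 90% CI at each timepoint.

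SAP section 4.10.5 lists the ECG times on Days 1 and 14 as "predose and at 0.5, 1.0, 1.5, 2.0, 2.5, 3.0, 4.0, 8.0, 12.0 and 24.0 hours (all +/- 15 mins" and adds: "The same assessment schedule is also required on Day -1, starting at a time similar to that planned for Days 1 and 14". Protocol section 10.4.4 says the same. Randomisation is on Day 1 (SAP section 4.4), so the Day -1 readings precede it. Section 8.11.5 uses them as the time-matched baseline for the descriptive summaries of Days 1 and 14. The by-timepoint models use them neither as covariate nor as outcome.

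**The concern.** One timepoint is a noisy measure of a woman's usual QTcF. Adjusting for it alone leaves part of the stable between-woman variation in the residual, although data that would remove more of it have been collected.

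What is at stake is the width of the by-timepoint intervals. Each dose has 15 active women. Section 8.11.7 opens the hysteresis exploration when an effect above 10 ms cannot be excluded in the by-timepoint analysis, so a wider interval makes that trigger more likely to fire for lack of precision alone.

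**Working it through.** **No figure to reproduce.** The only design calculation (SAP section 8.12) concerns power for log AUC, with SD 0.413. No SD, correlation or interval width is stated for any ECG parameter, so the variances below are assumptions.

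**Count of unused readings.** The schedule has 11 timepoints (predose plus 10). The Day -1 24 h reading must precede the Day 1 dose, so it roughly coincides with Day 1 predose: 11 - 1 = 10 further timepoints.

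**Model.** Change from baseline with the same baseline as covariate is equivalent to analysis of covariance on the post-dose value. Write s, d and e for the SDs between women, between days within a woman, and between readings within a day.

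- Variance of one reading: s² + d² + e².
- Variance of the mean of 10 Day -1 readings: s² + d² + e²/10.
- Covariance of that mean with any reading on another day: s².
- Covariance of Day 1 predose with a Day 1 post-dose reading: s² + d². With a Day 14 reading: s².

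**Central case, s = 15, d = 4, e = 7.** One reading has variance 225 + 16 + 49 = 290. The Day -1 mean has variance 225 + 16 + 4.9 = 245.9.

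Day 1 predose as the only covariate:

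- Day 1: 290 - 241²/290 = 89.7, SD 9.5 ms.
- Day 14: 290 - 225²/290 = 115.4, SD 10.7 ms.

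Both covariates (determinant 290 × 245.9 - 225² = 20,686):

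- Day 1 weights: (241 × 245.9 - 225²)/20,686 = 0.418 on predose and 225 × (290 - 241)/20,686 = 0.533 on the Day -1 mean. Residual 290 - 0.418 × 241 - 0.533 × 225 = 69.5 (unrounded weights), SD 8.3 ms.
- Day 14 weights: 225 × 20.9/20,686 = 0.227 and 225 × 65/20,686 = 0.707. Residual 290 - 225 × (0.227 + 0.707) = 79.8, SD 8.9 ms.

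**Interval width.** The PK analysis plan (section 3) names four cohorts, so 4 × 5 = 20 pooled placebo women. The 90% half-width is t(0.95, 75 df) × SD × √(1/15 + 1/20) = 1.665 × 0.3416 × SD = 0.569 × SD.

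| | Predose only | Plus Day -1 mean | Narrower by | Variance ratio |
|---|---|---|---|---|
| Day 1 | 5.4 ms | 4.7 ms | 12% | 89.7/69.5 = 1.29 |
| Day 14 | 6.1 ms | 5.1 ms | 17% | 115.4/79.8 = 1.45 |

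The variance ratio is the equivalent increase in women: 29% and 45%. A fifth cohort (25 placebo) multiplies every width by √(0.1067/0.1167) = 0.96 and leaves the percentages unchanged.

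**One slope for both days.** These figures let each day have its own weights. If a main-effect covariate settles midway between the Day 1 and Day 14 weights (0.095 and 0.087 away from each), the two-covariate residual variances rise by 290 × 0.095² - 2 × 225 × 0.095 × 0.087 + 245.9 × 0.087² ≈ 0.8. The single-covariate ones rise by 290 × 0.028² ≈ 0.2. The gains remain about 12% and 17%.

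**Range.** Over s = 12-18, d = 0-7 and e = 5-8 ms the gain is about 3-23% on Day 1 and 10-23% on Day 14. The extreme corner with no day-to-day variation (s = 18, d = 0, e = 5) reaches 25%. With between-day variance set at 10-20% of the total, the gain is about 4-9% on Day 1 and 9-14% on Day 14.

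**Less noisy readings.** With s = 15 and d = 4 but e = 3-4 ms, the predose-only half-width on Day 1 is 2.4-3.2 ms and the gain 5-7%. On Day 14 it is 3.9-4.4 ms and the gain about 15%.

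**Add, do not replace or pool.** With variance shares of 0.7 woman, 0.1 day and 0.2 reading, 3,000 simulated trials gave these standard errors for a Day 1 contrast: 0.204 with Day 1 predose alone, 0.189 with both covariates, and 0.216 with all 11 readings averaged into one. Across the day-effect splits tried, using the Day -1 mean alone multiplied the Day 1 standard error by 0.98 to 1.25.

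**The case against.** **Low stakes.** Section 8.11.7 may or may not be run, depending on results, and serves an exploratory objective. Its 10 ms conclusion comes from the exposure-response model at geometric mean Cmax, not from the by-timepoint contrasts. Failing to exclude 10 ms by timepoint leads only to visual inspection of curves and loops. The protocol's QTc stopping criterion (section 9.9) counts individual events. All of this stands. A reader might infer that a QT conclusion or a dose decision is unsafe or biased; the documents do not support that.

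**Assumed size.** This also stands. The documents do not say whether a timepoint averages replicate ECGs taken from the Holter recording. If it does, reading noise is smaller and the lower gains apply.

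**Baseline-by-time interactions.** The hot flash model includes "baseline (frequency of moderate/severe hot flashes at Week -1) and baseline-by-week interaction as covariates", so a reader might infer that the ECG model wrongly omits such terms. But that model has two post-dose weeks, and the other section 8.10 models likewise have two timepoints. The ECG model has about 20 on Days 1 and 14 alone. Interactions for two covariates would add dozens of parameters to a model whose possible non-convergence the SAP already anticipates, and no gain from them has been shown.

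**Outlier counts.** A reader might also want a new reference for the "changes from predose baseline of >30 or >60 msec" counts. These counts involve no model, so the precision argument does not carry over. A pooled reference would change their definition, and section 8.11.5 already tabulates such changes against time-matched Day -1 values for Days 1 and 14.

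**Unsettled baseline.** The opening of section 8.11.7 refers to a time-matched predose timepoint on Day 1, the By-Timepoint paragraph to Day 1 predose, and section 8.11.5 to time-matched Day -1. These need reconciling. The By-Timepoint paragraph is explicit for the models discussed here, but if it were changed to a Day -1 baseline, the gains above would not apply.

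**Different conditions on Day -1.** The fast specified for Days 1, 7 and 14 is not specified for Day -1 (protocol section 9.13.3). With the Day -1 mean as a covariate, a shift common to all arms cancels. Any variation between women in that shift would reduce the gain without biasing the contrast.

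**Conclusion.** The point holds as a modest loss of efficiency. The by-timepoint models ignore about 10 pre-randomisation ECG timepoints per woman, and adding their mean narrowed the 90% CI in every setting examined. In the central case (15/4/7 ms, 15 against 20 women) the saving is 0.7 ms on Day 1 and 1.0 ms on Day 14. The percentage depends on variances that the documents do not give: roughly 3-23% on Day 1 and 10-23% on Day 14 for reading SDs of 5-8 ms, or 5-7% and about 15% for 3-4 ms. The larger gain is on Day 14, where the Day 1 predose reading no longer shares a day effect with the outcome. The benefit is limited to the by-timepoint contrasts, if they are run, and to the trigger for the hysteresis exploration. The planned analysis remains valid without the change.

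**What to change.** In the By-Timepoint Analysis of SAP section 8.11.7, keep change from Day 1 predose as the response and Day 1 predose as a covariate. Add each woman's mean Day -1 value of the same parameter as a second covariate, as a main effect only, for QTcF, HR, PR, QRS, QT, RR and QTcB. Define the mean over the Day -1 readings other than the 24 h one, and state how a woman with missing Day -1 readings is handled. Do not replace the Day 1 predose value or pool it with the Day -1 readings. Leave the outlier counts as defined. The same edit could state whether each timepoint is an average of replicate ECGs.

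The cost is one sentence in the SAP and one extra parameter per model, with no additional ECGs, visits or women. The change should be fixed before unblinding.

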8.11.8 Physical Examinations

Physical examination findings will be presented in a subject listing.

8.11.9 Prior and Concomitant Medications and Procedures

Prior and concomitant medications will be coded using the World Health Organization Drug Dictionary (Version March 2017) and classified according to ATC codes levels 2 (therapeutic sublevel) and 4 (chemical sublevel). Prior medications are defined as all medications with start date before first dose date. Concomitant medications are defined as all medications with start

date on or after the first dose date. Medications with an incomplete start or end date will be considered concomitant unless it is clear from the incomplete start and end date that the medication started before the first dose date. Prior and concomitant medication data will be listed.

The concomitant procedures will also be listed.

8.12 Sample Size

The planned sample size is 20 subjects per cohort, with 15 active and 5 placebo. This is deemed enough to provide sufficient separation of exposures between dose groups and to allow for an assessment of safety versus dose group/exposure. Assuming a SD on the log scale of 0.413 for plasma AUC_{0-24} (based on Day 7 mean AUC_{0-24} data for 200 mg from study MNK111857), 15 active subjects per cohort provides close to 80% power at a type I error rate of 0.1 to detect a difference from one in the ratio of geometric means between the 2 highest possible dose levels (and greater than 90% power for the middle 2 dose levels) given the previously seen slightly greater than dose proportionality increase in systematic exposure. The placebo subjects are included primarily to provide a reference group for comparison of safety in the target population.

8.13 General Conventions for Tables, Listings and Figures

For summary tables, unless otherwise specified, the number of decimal places provided in the SAS output will be based on the accuracy of the least accurate value in the raw data as follows:

- n integer
- Arithmetic mean 1 decimal place more than the least accurate number in the raw data
- SD 2 decimal places more than the least accurate number in the raw data
- Median 1 decimal place more than the least accurate number in the raw data
- Minimum same number of decimal places as raw data
- Maximum same number of decimal places as raw data

9 TABLES, FIGURES, AND LISTINGS

Table/Figure Number	Table/Figure Name
Section 14.1	Demographic and Subject Characteristics Data Summaries
Table 14.1.1	Summary of Screening Outcome (All Subjects Set)
Table 14.1.2	Summary of Subject Disposition (All Randomized Set)
Table 14.1.3	Summary of Analysis Populations (All Randomized Set)
Table 14.1.4	Summary of Demographic Data (Safety Set)
Table 14.1.5	Summary of Baseline Physical Measurements (Safety Set)
Table 14.1.6	Summary of Study Drug Exposure (Safety Set)
Section 14.2	Efficacy/Pharmacokinetic/Pharmacodynamic Data Summaries
Section 14.2.1	Efficacy Data Summaries
Table 14.2.1.1.1	Summary of Daily Frequency of Hot Flashes - Twice Daily Diary (Full Analysis Set)
Table 14.2.1.1.2	Summary of Average Daily Frequency of Hot Flashes By Week and Change from Week -1 - Twice Daily Diary (Full Analysis Set)
Table 14.2.1.1.3	Statistical Analysis of Change from Week -1 in Average Daily Frequency of Moderate/Severe Hot Flashes - Twice Daily Diary (Full Analysis Set)
Table 14.2.1.2.1	Summary of Hot Flashes Average Severity - Twice Daily Diary (Full Analysis Set)
Table 14.2.1.2.2	Summary of Average Daily Severity of Hot Flashes by Week and Change from Week -1 - Twice Daily Diary (Full Analysis Set)
Table 14.2.1.2.3	Statistical Analysis of Change from Week -1 in Hot Flashes Average Daily Severity - Twice Daily Diary (Full Analysis Set)
Table 14.2.1.3.1	Summary of Hot Flashes Severity Score - Twice Daily Diary (Full Analysis Set)
Table 14.2.1.3.2	Summary of Average Daily Severity Score of Hot Flashes by Week and Change from Week -1 - Twice Daily Diary (Full Analysis Set)
Table 14.2.1.3.3	Statistical Analysis of Change from Week -1 in Hot Flashes

	Average Daily Severity Score - Twice Daily Diary (Full Analysis Set)
Table 14.2.1.4.1	Summary of Night Time Awakenings Secondary to Hot Flashes - Twice Daily Diary (Full Analysis Set)
Table 14.2.1.4.2	Summary of Average Daily Night Time Awakenings Secondary to Hot Flashes by Week and Change from Week -1 - Twice Daily Diary (Full Analysis Set)
Table 14.2.1.4.3	Statistical Analysis of Change from Week -1 in Average Daily Night Time Awakenings Secondary to Hot Flashes - Twice Daily Diary (Full Analysis Set)
Table 14.2.1.5.1	Summary of Total Number of Night Time Awakenings - Twice Daily Diary (Full Analysis Set)
Table 14.2.1.5.2	Summary of Average Daily Night Time Awakenings (Total) by Week and Change from Week -1 - Twice Daily Diary (Full Analysis Set)
Table 14.2.1.5.3	Statistical Analysis of Change from Week -1 in Average Daily Night Time Awakenings (Total) - Twice Daily Diary (Full Analysis Set)
Table 14.2.2.1.1	Summary of Daily Frequency of Hot Flashes - Continuous Hot Flash Diary (Full Analysis Set)
Table 14.2.2.1.2	Summary of Average Daily Frequency of Hot Flashes by Week - Continuous Hot Flash Diary (Full Analysis Set)
Table 14.2.2.1.3	Statistical Analysis of Change from Day -1 in Daily Frequency of Moderate/Severe Hot Flashes - Continuous Hot Flash Diary (Full Analysis Set)
Table 14.2.2.2.1	Summary of Night Time Awakenings Secondary to Hot Flashes - Continuous Hot Flash Diary (Full Analysis Set)
Table 14.2.2.2.2	Summary of Average Daily Night Time Awakenings Secondary to Hot Flashes by Week - Continuous Hot Flash Diary (Full Analysis Set)
Table 14.2.2.2.3	Statistical Analysis of Change from Day -1 in Daily Night Time Awakenings Secondary to Hot Flashes - Continuous Hot Flash Diary (Full Analysis Set)

Table 14.2.2.3.1	Summary of Night Time Awakenings (Total) - Continuous Hot Flash Diary (Full Analysis Set)
Table 14.2.2.3.2	Summary of Average Daily Night Time Awakenings (Total) by Week - Continuous Hot Flash Diary (Full Analysis Set)
Table 14.2.2.3.3	Statistical Analysis of Change from Day -1 in Daily Night Time Awakenings (Total) - Continuous Hot Flash Diary (Full Analysis Set)
Table 14.2.3.1	Summary of Daily Frequency of Hot Flashes Detected by the Device - Sternal Skin Conductance (Full Analysis Set)
Table 14.2.3.2	Summary of Average Daily Frequency of Hot Flashes Detected by the Device by Week - Sternal Skin Conductance (Full Analysis Set)
Table 14.2.3.3	Statistical Analysis of Change from Day -1 in Daily Frequency of Hot Flashes Detected by the Device - Sternal Skin Conductance (Full Analysis Set)
Table 14.2.4.1	Summary of Luteinizing Hormone AUC0-8 and Change from Day -1 (Full Analysis Set)
Table 14.2.4.2	Statistical Analysis of Luteinizing Hormone AUC0-8 Change from Day -1 (Full Analysis Set)
Figure 14.2.1.1.1	Mean (+/- SE) Daily Frequency of Hot Flashes - Twice Daily Diary (Full Analysis Set)
Figure 14.2.1.2.1	Mean (+/- SE) Daily Hot Flashes Average Severity - Twice Daily Diary (Full Analysis Set)
Figure 14.2.1.3.1	Mean (+/- SE) Daily Hot Flashes Severity Score - Twice Daily Diary (Full Analysis Set)
Figure 14.2.1.4.1	Mean (+/- SE) Night Time Awakenings Secondary to Hot Flashes - Twice Daily Diary (Full Analysis Set)
Figure 14.2.1.5.1	Mean (+/- SE) Night Time Awakenings (Total) - Twice Daily Diary (Full Analysis Set)
Figure 14.2.2.1.1	Mean (+/- SE) Daily Frequency of Hot Flashes - Continuous Hot Flash Diary (Full Analysis Set)
Figure 14.2.2.2.1	Mean (+/- SE) Night Time Awakenings Secondary to Hot Flashes

	- Continuous Hot Flash Diary (Full Analysis Set)
Figure 14.2.2.3.1	Mean (+/- SE) Night Time Awakenings (Total) - Continuous Hot Flash Diary (Full Analysis Set)
Figure 14.2.3.1	Mean (+/- SE) Daily Frequency of Hot Flashes Detected by the Device - Sternal Skin Conductance (Full Analysis Set)
Section 14.3	Safety Data Summaries
Section 14.3.1	Displays of Adverse Events
Table 14.3.1.1	Overall Summary of Treatment-Emergent Adverse Events (Safety Set)
Table 14.3.1.2	Summary of Treatment-Emergent Adverse Events by System Organ Class and Preferred Term (Safety Set)
Table 14.3.1.3	Summary of Treatment-Emergent Adverse Events by Reported Severity (Safety Set)
Table 14.3.1.4	Summary of Treatment-Emergent Adverse Events by Relationship to Study Drug (Safety Set)
Section 14.3.2	Listings of Deaths, Other Serious and Certain Significant Adverse Events
Table 14.3.2.1	Listing of Adverse Events Leading to Death (Safety Set)
Table 14.3.2.2	Listing of Serious Adverse Events (Safety Set)
Table 14.3.2.3	Listing of Adverse Events Resulting in Discontinuation of Study or Treatment (Safety Set)
Table 14.3.2.4	Listing of Treatment-Emergent Adverse Events of Dehydration (Safety Set)
Section 14.3.4	Abnormal Laboratory Value Listing
Table 14.3.4.1	Listing of Abnormal Laboratory Results (Safety Set)
Section 14.3.5	Additional Safety Data Summaries
Table 14.3.5.1	Absolute and Change from Baseline for Clinical Laboratory Parameters (Chemistry, Hematology, Lipids and Coagulation)

	(Safety Set)
Table 14.3.5.2	Absolute and Change from Baseline for Laboratory Hormones Results (Safety Set)
Table 14.3.5.3	Laboratory Shift in Normal Range Indicator by Category (Chemistry, Hematology, Lipids and Coagulation) (Safety Set)
Table 14.3.5.4	Laboratory Shift in Normal Range Indicator of Hormones Results (Safety Set)
Table 14.3.5.5	Absolute and Change from Baseline Vital Signs (Safety Set)
Table 14.3.5.6	Summary Statistics of 12-Lead ECG Values and Change from Baseline (Safety Set)
Table 14.3.5.7.1.1	Summary of Daily Maximum QTcB and QTcF Interval Results (Safety Set)
Table 14.3.5.7.1.2	Summary of Overall Maximum Post-Baseline QTcB and QTcF Interval Results (Safety Set)
Table 14.3.5.7.1.3	Summary of Overall Maximum Predose QTcB and QTcF Interval Results (Safety Set)
Table 14.3.5.7.2.1	Summary of Daily Maximum Change From Baseline QTcB and QTcF Interval Results (Safety Set)
Table 14.3.5.7.2.2	Summary of Overall Maximum Change From Baseline QTcB and QTcF Interval Results (Safety Set)
Table 14.3.5.7.3	Abnormal Interpretation for 12-Lead ECG (Safety Set)
Table 14.3.5.8.1	Analysis for Arrhythmias by Continuous Holter Monitoring by Day (Safety Set)
Table 14.3.5.8.2	Analysis for Post-Baseline Arrhythmias by Continuous Holter Monitoring (Safety Set)

Listing Number

Listing Name

Section 16.1.7

Randomization

Listing 16.1.7

Randomization Allocation (All Randomized Set)

Section 16.2.1	Discontinued Subjects
Listing 16.2.1.1	Screening Outcome (All Subjects Set)
Listing 16.2.1.2	Subject Disposition (Safety Set)
Section 16.2.2	Protocol Deviations
Listing 16.2.2	Protocol Deviations (All Randomized Set)
Section 16.2.3	Subjects Excluded from Analysis
Listing 16.2.3	Exclusions from Analysis Populations (All Randomized Set)
Section 16.2.4	Demographic Data
Listing 16.2.4.1	Demographics Data (Safety Set)
Listing 16.2.4.2	Physical Measurements (Safety Set)
Listing 16.2.4.3	Inclusion/Exclusion Criteria (Safety Set)
Listing 16.2.4.4	Consent Information (Safety Set)
Listing 16.2.4.5	Medical and Surgical History (Safety Set)
Listing 16.2.4.6	Prior and Concomitant Medications (Safety Set)
Listing 16.2.4.7	Concomitant Procedures (Safety Set)
Listing 16.2.4.8	Visit Dates (Safety Set)
Section 16.2.5	Compliance and/or Drug Concentration Data
Listing 16.2.5.1	Study Drug Dosing (Safety Set)
Section 16.2.6	Individual Efficacy Data
Section 16.2.6.1	Individual Efficacy Response Data
Listing 16.2.6.1.1.1	Hot Flash Twice Daily Diaries Data (Full Analysis Set)
Listing 16.2.6.1.1.2	Hot Flash Twice Daily Diaries Data - Daily Derivation (Full Analysis Set)
Listing 16.2.6.1.1.3	Hot Flash Twice Daily Diaries Data - Weekly Derivation (Full Analysis Set)
Listing 16.2.6.1.2.1	Continuous Hot Flash Diary Data (Full Analysis Set)
Listing 16.2.6.1.2.2	Continuous Hot Flash Diary Data - Daily Derivation (Full Analysis Set)

Listing 16.2.6.1.2.3	Continuous Hot Flash Diary Data - Weekly Derivation (Full Analysis Set)
Listing 16.2.6.1.3.1	Data Collection of the Skin Conductance Monitor (Full Analysis Set)
Listing 16.2.6.1.3.2	Skin Conductance Monitor Hot Flashes (Full Analysis Set)
Listing 16.2.6.1.3.3	Skin Conductance Monitor Hot Flashes Detected by the Device - Derivation (Full Analysis Set)
Listing 16.2.6.1.4	Luteinizing Hormone Data (Full Analysis Set)
Section 16.2.7	Adverse Event Listings
Listing 16.2.7.1	All Adverse Events (Safety Set)
Listing 16.2.7.2	Verbatim to Preferred Term Mapping of All Adverse Events
Section 16.2.8	Individual Laboratory Measurements by Subject
Listing 16.2.8.1	Normal Ranges for Laboratory Data
Listing 16.2.8.2	Clinical Laboratory Data by Category (Chemistry, Hematology, Lipids and Coagulation) (Safety Set)
Listing 16.2.8.3	Hormones Results (Safety Set)
Listing 16.2.8.4	Urinalysis Results (Safety Set)
Listing 16.2.8.5	Vital Signs (Safety Set)
Listing 16.2.8.6	12-Lead Electrocardiogram Results (Safety Set)
Listing 16.2.8.7	Holter Electrocardiogram Monitoring (Safety Set)
Listing 16.2.8.8	Physical Examination (Safety Set)
Listing 16.2.8.9	Investigator Comments (Safety Set)

VERSION HISTORY

Version	Date	List principal changes from previous version
2.0	27FEB2017	
- Section 4.1 and 4.10.5 has been changed to take into account the changes in the protocol version 4.0 dated 13DEC2016.- The night time awakenings analyses are now separated in 2 groups: NTA secondary to hot flashes and NTA, Total- The baseline for ECG is now defined as the time matched assessment done at Day -1- The maximum QTcB and QTcF values are analysed daily and overall.
1.0	01DEC2016	NA. Initial Version

STATISTICAL ANALYSIS PLAN FOR PHARMACOKINETICS

Protocol RELENT-1

EVALUATION OF THE PHARMACOKINETICS AND SAFETY OF NT-814 IN POST-
MENOPAUSAL WOMEN WITH VASOMOTOR SYMPTOMS

Version: Final 1.0

Date: 5 May 2017

REVISION HISTORY

[figure not shown]
Version	Version Date	Author	Summary of Changes Made
Draft 1.0	April 10, 2017	PPD	New Document
Final 1.0	May 5, 2017	PPD	

SIGNATURE PAGE - NERRE THERAPEUTICS LTD.

Declaration

The undersigned has/have reviewed and agree to the statistical analyses and procedures of this clinical study, as presented in this document.

PPD

Date (DD Mmm YYYY)

8th May 2017

[figure not shown]
Date (DD Mmm YYYY)

SIGNATURE PAGE - NERRE THERAPEUTICS LTD.

Declaration

The undersigned has/have reviewed and agree to the statistical analyses and procedures of this clinical study, as presented in this document.

PPD

